### OVERSIGHT RESPONSIBILITIES

Oversight of the trial is provided by the Principal Investigator (PI), [name] and [name].

#### MONITORING PROCEDURES

[name] assures that informed consent is obtained prior to performing any research procedures, that all subjects meet eligibility criteria, and that the study is conducted according to the IRB-approved research plan.

Study data are accessible at all times for the PI and co-investigators to review. The PI and co-investigators review(s) study conduct including accrual, screen failures, protocol deviations on a quarterly basis. The PI and co-investigators review AEs individually in real-time and in aggregate on a quarterly basis. The PI and co-investigators review(s) serious adverse events (SAEs) in real-time. The PI ensures all protocol deviations, AEs, and SAEs are reported to the IRB according to the applicable regulatory requirements.

#### COLLECTION AND REPORTING OF SAEs AND AEs

For this study, the following standard AE definitions are used:

**Adverse event:** Any unfavorable and unintended sign (including an abnormal laboratory finding), symptom or disease temporally associated with the use of a medical treatment or procedure, regardless of whether it is considered related to the medical treatment or procedure.

**Serious Adverse Event:** Any AE that results in any of the following outcomes:

- \* Death
- \* Life-threatening
- \* Event requiring inpatient hospitalization or prolongation of existing hospitalization
- \* Persistent or significant disability/incapacity

AEs are graded according to the following scale:

**Mild:** An experience that is transient, & requires no special treatment or intervention. The experience does not generally interfere with usual daily activities. This includes transient laboratory test alterations.

**Moderate:** An experience that is alleviated with simple therapeutic treatments. The experience impacts usual daily activities. Includes laboratory test alterations indicating injury, but without long-term risk.

**Severe:** An experience that requires therapeutic intervention. The experience interrupts usual daily activities. If hospitalization (or prolongation of hospitalization) is required for treatment it becomes an SAE.

The study uses the following AE attribution scale

**Not related:** The AE is clearly not related to the study procedures (i.e., another cause of the event is most plausible and/or a clinically plausible temporal sequence is inconsistent with the onset of the event).

**Possibly related:** An event that follows a reasonable temporal sequence from the initiation of study procedures, but that could readily have been produced by a number of other factors.

**Related:** The AE is clearly related to the study procedures.

AEs are identified during hospital admission, when potential AEs are assessed through a review of the hospital chart on a daily basis and a physical examination of the subject.

SAEs and specific procedure-associated AEs are reported to the VCU Institutional Review Board (IRB) within 24 hours. In addition, all AEs are reported according to the VCU IRB AE reporting guidelines.

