## Secondary Data/Specimen Details

1. Describe the source(s) and nature of the information/specimens being obtained. This response should:

- Identify where the data/specimens will come from (e.g., another researcher's registry, pathology lab, commercial source, medical records, etc.); and
- List what types of specimens will be obtained (when applicable); and/or
- List all data elements that will be obtained (when applicable). A data collection form or other documentation may be uploaded and referenced here.

The data being collected includes pain medicine administered for the first 48 hours after surgery. There is a data collection form uploaded in documents. Visual analogue scores are not being collected any longer due to poor reliability.

2. Describe whether any agreement exists between you and data/specimen provider that states you will never have access to the ability to identify the participants (i.e. access to identifiers or the code key) and that you will not attempt to re-identify individuals.

Each subject has a subject number that is being assigned by RedCap (the index number) used as a code. This number is used on the data collection form. Once all data is collected and entered into RedCap this form will be destroyed. Once all data is collected and analyzed all identifiers will be removed from RedCap.

The patient identifiers are in redcap and will not be used in any way that would identify the patient by name. The data will be used in aggregate when reporting the results.

3. When the information/specimens were originally collected, did individuals provide consent for secondary research use of their data/specimens (i.e. consent to another research study or to a research registry)?

Yes

No

HM20004125 [name]  
Do Intraoperative Periarthicular Injections Improve Postoperative Pain Control in Patients Receiving Duramorph? A Prospective, Double  
Blinded, Randomized Controlled Trial

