A full review of the patient's medical record, including allergies, will be performed to minimize allergic and other adverse drug reactions. The periarthicular injection will be placed in a region away from nerves so as to prevent temporary or permanent weakness/numbness.

In patients who do not receive the periarthicular injection, they will continue to receive other important components of the perioperative multimodal analgesia protocol.

Patients are monitored at least daily by medical staff after undergoing TKR. Nursing protocol monitors pain scores and pain acceptance rates on an hourly basis post-surgically. Any side effects will be noted during this monitoring process. As previously noted, the risks in this study are notably, potential pain by not receiving the per-articular joint injection, since all patients who are NOT enrolled in the study will likely receive the injection.

3. Describe any potential risks or harms to a community or a specific population based on study findings (e.g. information that could be stigmatizing or derogatory):

None

4. Where appropriate, discuss provisions for ensuring necessary medical, professional, or psychological intervention in the event of adverse events to the subjects:

If there is any adverse reaction to the injection this will be handled by the orthopedic physicians who are caring for the patient during their surgery.

5. Describe criteria for when the investigator would withdraw an individual participant from the study; such as safety or toxicity concerns, emotional distress, inability to comply with the protocol, etc.:

If there is a toxicity or adverse reaction concern, the patient will be withdrawn from data collection and treated appropriately according to current medical guidelines and standards.

Any toxicity event or adverse effects will be managed with the use of fluids, and medications such as anti-emetics. Patient level of monitoring may be increased to allow for closer observation and treatment. Other treatment interventions will be managed with additional interventions as deemed necessary by the treating physicians.

6. Summarize any pre-specified criteria that would trigger the investigator/sponsor/monitoring committee to stop or change the study protocol due to safety concerns:

NA

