##### DATA ANALYSIS PLANS

There will be no interim analysis for safety, efficacy or both. Due to the low risk of this study—currently the surgeons involved in this study have used this multimodal periaricular injection for the last 15 years and have noted no adverse events that could be attributed to the injection—an interim analysis was deemed not necessary for safety. Additional considerations were the increased cost of more subjects when performing an interim analysis. Expected AEs will be assessed after each procedure and during the subsequent hospitalization and discussed at the quarterly research meetings (as noted above). Any unexpected AE will be reported to the VCU IRB within 24 hours as required by the VCU IRB. There are no planned stopping rules.

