All patient interactions will be done in a private examination room or practitioner offices at the Stony Point Ambulatory Center, ACC clinics, NOW center (Short Pump) or the perisurgical areas. These offices are all private, with doors that close. No patient will be approached in the waiting area. No images will be taken.

Once data collection is complete, all data will be de-identified and there will be no risk to the patient. Prior to de-identification, all data will be housed on a password protected computer in a locked office at the VCU Medical Center (within RedCap).

All patients (whether receiving the active injection or the placebo) will have the injection prepared in the investigational pharmacy and delivered to the OR either the day prior to or the morning of the surgery. The labels on the syringes will not note the treatment group, thus keeping the blinding. This is the only research activity while the patient is hospitalized. After the surgical procedure, all activities will be standard post-op treatment. The research activity will occur later via chart review (mg of pain medicine)

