### HIPAA Privacy Board Requirements

For guidance, see <https://www.vcuhealth.org/our-story/who-we-are/compliance-services/compliance-services>

1. \* Select the source of the Individually Identifiable Health Information. See help text for definitions.
- PHI associated with or derived from (i.e. obtained from or entered into) VCU Health medical records or VCU Dental Care records
  - Research Health Information (RHI) created or received by a study and kept solely in study records (e.g. self reported or the result of research tests and not entered into health records)
  - PHI associated with or derived from (i.e. obtained from or entered into) a non-VCU HIPAA covered entity's health records

2. \* Summarize the types of health information that will be obtained or used in this research. Do not describe only the identifiers that you will collect or use during the study.  
Patients will be identified at their preoperative office visits with their surgeon. There will be no searching of the information system to find suitable patients; these patients are all being seen as part of their treatment/consultation for knee arthroplasty.

We will use patient's names, medical record numbers, and the dates of the operative procedures to identify those who have consented to be randomized as well as to review the required information in their electronic medical record. Only those points of interest will be included in the post hospitalization chart review. A master list will be kept on a password-protected computer in a locked office at the VCU Medical Center system.

3. \* Describe the source(s) of the protected health information (e.g. information or which clinical databases):  
The VCU Medical Center electronic medical record.

4. \* Does the PI certify that this study's access to and use of the protected health information is limited to the minimum amount necessary to be able to effectively conduct the research?
- Yes  No

5. \* Select all pathways this research will employ to use or access PHI (selections will branch):
- De-identified Data (none of the 18 identifiers are recorded or associated with the research data)
  - Limited Data Set
  - Waiver of Authorization
  - Partial Waiver of Authorization (temporary waiver for recruitment purposes and/or waiver of some elements of Authorization)
  - Signed Authorization Combined with Consent Form
  - Signed Authorization as Stand-Alone Form

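### Active adverse-event ascertainment ends at discharge, so readmission and the persistence of a disability, both within the plan's own SAE definition, would be captured only by chance

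*Combined protocol and SAP*

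**What the plan says.** Under Collection and Reporting of SAEs and AEs, the method and the window appear in one sentence: "AEs are identified during hospital admission, when potential AEs are assessed through a review of the hospital chart on a daily basis", with a physical examination added. The Data Analysis Plans section agrees: "Expected AEs will be assessed after each procedure and during the subsequent hospitalization".

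The same collection section defines a serious adverse event by four outcomes: death; a life-threatening event; "Event requiring inpatient hospitalization or prolongation of existing hospitalization"; and "Persistent or significant disability/incapacity". Under Risks, Discomforts, Potential Harms and Monitoring, the injection is to be placed away from nerves "so as to prevent temporary or permanent weakness/numbness". That section also calls temporary nerve palsy the most common adverse effect, and very rare.

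Three statements describe data collection more broadly.

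- Secondary Data/Specimen Details: "The data being collected includes pain medicine administered for the first 48 hours after surgery".
- The closing free-text answer on the Privacy page: "After the surgical procedure, all activities will be standard post-op treatment". The research work that follows is described there as chart review for milligrams of pain medicine.
- HIPAA Privacy Board Requirements: "Only those points of interest will be included in the post hospitalization chart review". The items are not listed there.

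**The concern.** The window for seeking events is shorter than some of the events the plan defines as serious. A patient who is already admitted can meet the new-hospitalisation limb only by being readmitted, which happens after the window closes. Whether a weakness or numbness is temporary or permanent can be settled only by looking again later, and nothing planned does so.

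What is at stake is the harms information from the trial. The documents plan one blinded, randomised comparison of the injection with placebo, and the risk section says that the risks named in the consent form cannot be quantified. There is no interim analysis and there are no stopping rules. The investigators' own real-time and quarterly review is therefore the only look at accumulating harms, and after discharge it sees only what surfaces incidentally.

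**Working it through.** The plan gives no figure on this point to reproduce, so the check sets its sections side by side.

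**Step 1: the four SAE criteria against the stated window.**

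| Criterion | Seen during the admission | Planned detection after discharge |
|---|---|---|
| Death | Yes | None |
| Life-threatening event | Yes | None |
| Hospitalisation: prolonged stay | Yes | Not applicable |
| Hospitalisation: new admission | No, the patient is already in hospital | None |
| Disability: significant | Yes | None |
| Disability: persistent | Persistence needs later observation | None |

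Each criterion can be met in some form during the admission. Two limbs, new admission and persistence, depend on observation after it.

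**Step 2: does any other section supply that observation?**

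- *Monitoring Procedures* has the investigators review adverse events in real time and quarterly, with no end date. This governs what is done with known events. It is not a means of finding them.
- *Data Analysis Plans* requires unexpected events to be reported within 24 hours, also with no end date. Again this is reporting, not detection.
- *Risks, Discomforts, Potential Harms and Monitoring* describes nursing and medical monitoring after surgery. It describes no check after discharge.
- *Privacy* names only pain medicine as the content of the later chart review.
- *HIPAA Privacy Board Requirements* provides for a chart review after hospitalisation but names neither adverse events nor readmissions.
- *Secondary Data/Specimen Details* refers to an uploaded data collection form, which is not among the documents. It may hold adverse-event fields, but nothing in the text says that it does or gives a later window.

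None of these adds active ascertainment after discharge.

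**Step 3: can the gap be closed later?** Data Confidentiality and Storage says the linkage key is destroyed once data collection is complete. Secondary Data/Specimen Details puts removal of identifiers after collection and analysis. If the earlier point applies and collection is taken to end with the 48-hour medication data, records of the last patients could no longer be linked to later events.

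**Step 4: size.** If a share f of events arises after discharge, in-hospital ascertainment can capture at most (1 − f) of the total, apart from incidental reports. The documents give neither f nor the length of stay. Any f from 0 to 1 is compatible with them, so no estimate is offered.

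**The case against.** The strongest reply is that the SAE wording is a standard definition, and such a definition does not promise that every limb will be actively sought. Both disputed criteria offer alternatives that can be met in hospital. Review and reporting duties have no cut-off, so a later event that reaches the team would still be handled. The trial's hypothesis concerns narcotic use and its objective pain control, and no safety endpoint or safety conclusion is planned. The injection is given once, is described as standard of care for those who decline, and has been used by these surgeons for 15 years with no adverse events attributed to it. The weakness and numbness wording explains where the injection is placed and does not define an outcome.

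Much of this stands, and it rules out several stronger readings.

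- A reader might infer that the listed SAE criteria cannot be observed at all. The table above shows otherwise, and incidental capture after discharge remains possible.
- A reader might infer that later harms would be counted as absent. The documents contain no adverse-event analysis, denominator or counting rule, so they do not say this.
- A reader might expect renal toxicity or gastrointestinal bleeding, both listed as expected events, to appear after discharge. The documents give no onset times, so this would be an assumption.
- A confidence bound for zero events in 64 patients might seem to measure the problem. It reflects the sample size and would be the same for any length of follow-up.

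What the reply does not supply is a means of detection after discharge. The in-hospital limit is a stated rule, given in two places, and not merely an omitted detail. The surgeons' past experience is uncontrolled and does not replace ascertainment in two blinded arms.

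**Conclusion.** The point holds in this form: active ascertainment is confined to the surgical admission, and no window or readmission check is defined after it. New hospitalisation and the persistence of a disability would be captured only by chance. Prolonged stay, significant disability, and in-hospital death or life-threatening events are covered.

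The size is unknown, for want of the length of stay and the share of events after discharge. The conclusion rests on the text supplied; an adverse-event section in the uploaded data collection form could narrow it. The efficacy comparison and the 64 per group are unaffected. The matter deserves an amendment because the rule limits what the trial can say about harms and the remedy is cheap.

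**What to change.** 1. In Collection and Reporting of SAEs and AEs and in Data Analysis Plans, state a fixed time after surgery, covering the first routine postoperative visit, up to which AEs and SAEs are ascertained. Apply it identically in both arms, with the assessors still blinded.
2. In HIPAA Privacy Board Requirements, name AEs, readmissions and charted persistent weakness or numbness among the items of the chart review after hospitalisation. Bring the Privacy page's description of that review into line.
3. In Data Confidentiality and Storage, keep the linkage key until that review is done, and reconcile the two statements on when identifiers are removed.
4. Reconcile the extended ascertainment with the withdrawal answer in the risk section, which ends data collection for a patient with a toxicity or adverse-reaction concern and could cut short the record of a known event.
5. If ascertainment stays in hospital only, label any reported adverse-event results as in-hospital events.

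The cost is an amendment and one later pass through records the team already accesses, with no added patient, visit or test. Identifiers are kept longer, and events treated at other hospitals may still be missed.

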#### MANAGEMENT OF RISKS TO SUBJECTS

##### Expected AEs

Expected AEs (although risk is very low based on published research and 15 years of experience) associated with the drugs used in the periaricular injection includes:

1. Ropivacaine
  - a. Cardiotoxicity
  - b. Hepatotoxicity
  - c. Nausea
  - d. Hypotension
  - e. Vomiting
  - f. Bradycardia
  - g. Tinnitus
  - h. Dizziness
  - i. Dry mouth
2. Ketorolac
  - a. Platelet dysfunction
  - b. Renal toxicity
  - c. Gastrointestinal bleeding
3. Epinephrine
  - a. Hypertension
  - b. Tachycardia
  - c. Arrhythmias
4. Clonidine
  - a. Hypotension
  - b. Bradycardia
  - c. Pruritis
  - d. AV block
  - e. Sedation
  - f. Dizziness
  - g. Dry mouth

##### AE Management

Any AEs will be managed with the use of fluids, and medications such as anti-emetics. Patient level of monitoring may be increased to allow for closer observation and treatment. Other treatment interventions will be managed with additional interventions as deemed necessary by the treating physicians.

##### DATA ANALYSIS PLANS

There will be no interim analysis for safety, efficacy or both. Due to the low risk of this study—currently the surgeons involved in this study have used this multimodal periaricular injection for the last 15 years and have noted no adverse events that could be attributed to the injection—an interim analysis was deemed not necessary for safety. Additional considerations were the increased cost of more subjects when performing an interim analysis. Expected AEs will be assessed after each procedure and during the subsequent hospitalization and discussed at the quarterly research meetings (as noted above). Any unexpected AE will be reported to the VCU IRB within 24 hours as required by the VCU IRB. There are no planned stopping rules.

##### PLAN FOR DATA MANAGEMENT

Compliance of regulatory documents and study data accuracy and completeness will be maintained through an internal study team quality assurance process.

Confidentiality throughout the trial is maintained by all patient information being maintained in the Red Cap database which is only accessible by members of the study team. No paper documents are kept.

## Privacy

Privacy refers to an individual's right to control how others view, record, or obtain information about them. When privacy is violated it can involve such things as

- Being asked personal questions in a public setting;
- Being publicly identified as having a particular characteristic or diagnosis;
- Being seen entering a place that might be stigmatizing;
- Being photographed, videotaped or observed without consent;
- Disclosure of personal information to unauthorized people

Privacy is not the same as confidentiality because privacy protections apply to people, and confidentiality protections apply to data. Confidentiality protections should be described on the Data Confidentiality page of this form, not here.

**Instructions for this page:**

Select all the applicable ways that the research team will protect participants' privacy throughout the course of the study. Not all will be applicable to every study.

To elaborate on any response, also click the "Other Protections" checkbox to provide further explanation in the last free-text question.

Read the entire page before filling out the form.

